6.5 Interim Analyses and Data Monitoring

No formal interim analyses were planned nor carried out for this study. The study was overseen by a Data and Safety Monitoring Board (DSMB) that reviewed the pooled and by-treatment subject disposition, study conduct and safety data approximately every 6 months.

6.6 Multiple Testing

Two-sided p-values will be reported. For the co-primary endpoints, a Bonferonni adjustment for multiplicity will be applied. For all other endpoints, no adjustments for multiplicity will be made. Thus, p-values for secondary and exploratory outcomes will be interpreted with caution (note that this is a departure from the protocol). Means and standard errors will be provided to summarize treatment differences for efficacy end points.

7 Summary of Study Data

Descriptive summary statistics will be derived for all data at baseline, separately by treatment sequence and overall. For efficacy, exploratory and safety data, data will be presented by treatment group. Treatment group will be characterized as "Varenicline" and "Placebo"; for pooled summaries, "Overall" will be used as the column heading. All tables will be annotated with the total population size relevant to that table/treatment, including any missing observations.

For continuous variables, mean, standard deviation, median, interquartile range, minimum and maximum will be reported. For categorical variables, number and percentages will be reported (excluding missing values). Graphical methods will be heavily used in this pilot study to assess the pattern of response over time for key variables and to assess the relationships among variables.

7.1 Subject Disposition

The number of participants approached for study participation, the number consented and the number who did not consent (including reasons: screen failures, refusals) will be summarized in a CONSORT diagram. The number of participants who dropped out prior to randomization, and the reasons for dropout, will be summarized. The number randomized and treated and the number who dropped out by weeks 3, 6, and 9 will be provided, as well as the number in each of the analysis populations (i.e., ITT, Compliant, Safety). Reasons for post-treatment dropout will be provided.

7.2 **Protocol Deviations**

Major protocol deviations that exclude a patient from the Compliant Per Protocol Population are described in section 8.3.2. A listing of protocol deviations that exclude participants from the Compliant Population will be provided. A listing of participants who receive exemptions for study eligibility will also be provided.

7.3 Demographic and Baseline Variables

Demographic variables include: age at consent (defined as a continuous variable, e.g., 52.6 years), sex, race and ethnicity.

Baseline is defined as pre-treatment measures. Baseline variables include:

- Age at diagnosis (years)
- MDS-UPDRS III total score
- GDS score
- MoCA score

7.4 Treatment Compliance

A listing of compliance with study medication (# of doses taken by day) was provided by treatment and period.

8 Efficacy Analyses

8.1 Primary, Secondary and Exploratory Efficacy Analyses

For the Crossover study, linear mixed models containing treatment sequence, treatment period, treatment group, and dependent-variable baseline value, with participant within treatment sequence as a random effect, will be used for analysis of continuous outcomes. To compare differences between VCN and placebo, a test for carryover based on the sequence effect will be conducted using patient with sequence as the error term. Results will be presented as least squares (LS) mean and standard error (SE). The co-primary endpoints will be tested at the 2-sided, 0.025, significance level. All other tests will be based on a 2-sided significance level of 0.05; no adjustments will be made for additional multiple comparisons. Primary, secondary and key efficacy endpoints will be analyzed in all randomized participants (intention-to-treat [ITT] population) and in the Compliant Population.

Additional sensitivity analyses will be performed for UPDSR-III total and PIG subscale scores, where baseline degree of total cortical cholinergic denervation (from PET scans) and baseline degree of striatal dopamine denervation (from PET scans) were incorporated as covariates in separate models. These models will also be run for gait speed end points.

9 Safety Analyses

Safety endpoints will be analyzed in all randomized participants who received at least one dose of study medication (Safety Population). We will include adverse events that occurred in the washout period with the treatment given in period one.

Safety data, including adverse events (AEs) and the Columbia-Suicide Severity Rating Scale (C-SSRS), will be summarized descriptively by treatment group for the Safety Population.

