nAChR expression will be measured in vivo with [F]flubatine. Subjects will receive varying VCN doses. [F]Flubatine imaging will be done 10 days after initiation of VCN administration and 5 days after VCN discontinuation (**Figure 4**). The difference between [F]flubatine binding before and after VCN discontinuation will be measured to assess  $\alpha 4\beta 2^*$  nAChR occupancy. Receptor occupancy will be assessed in regions exhibiting high  $\alpha 4\beta 2^*$  nAChR expression; thalamus, striatum, and cerebellum, as results are likely to be more variable in regions with lower  $\alpha 4\beta 2^*$  nAChR expression. Based on prior animal and human studies, 7-10 days

is adequate to induce receptor upregulation (91-95). VCN has a  $t_{1/2}$  of ~24 hours and 10 days will be adequate to attain equilibrium and induce upregulation. VCN pharmacokinetics (PK) do not change with age and absorption is unaffected by food (96). Five days is adequate to clear VCN.  $T_{max}$  is 2-4 hours post oral administration. The first scan will occur in the afternoon of day 10 after the morning VCN dose to avoid peak dose effects which could increase variance.

The recommended clinical VCN dose schedule is 0.5 mg per day for 3 days, followed by 0.5 mg bid for 4 days, followed by 1 mg bid. Mocking et al. recently reported positive neuropsychological results of subacute VCN

treatment (0.5 mg/day for 3 days, then 1 mg/day for 4 days) in normal controls (79). Because we are administering VCN to a clinical population and not young, healthy controls, we propose lower initial doses than Mocking et al. We will start with 0.25 mg/day on a subacute treatment schedule of 10 treatment days. A potential acute side effect of VCN is nausea, though this is unusual in non-smokers with doses below 1 mg per day. To reduce the chance of nausea or other side-effects, we will use a series of escalating dose schedules (**Appendix 2**). VCN will be prepared by the U-M Health System Research Pharmacy. VCN pills are small, easily encapsulated in gelatin capsules, and will be dispensed in blister packs to facilitate administration and compliance monitoring. The initial maximum dose studied will be 0.25 mg/day. Subsequent, projected maximum doses are 0.25 po bid, 0.5 mg po bid, and 1 mg po bid (if needed). Twice daily dosing is used to minimize peak dose effects. We anticipate 3 dose points, each consisting of 3 participants (total of 9

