ABT-089 on levodopa induced dyskinesias close to 2 weeks after dose cessation, well beyond the t1/2 of this agent. This wash-out interval was used also in the recent VCN AD trial (89). The randomization schedule and process will be prepared by the **Biostatistics and Data Management Core.** Blinded, encapsulated study drug (VCN and placebo) will be supplied by the U-M Research Pharmacy to the study coordinator. The latter will dispense the study medication. Subjects will be evaluated in the University of Michigan Functional Neuroimaging, Cognitive and Mobility Laboratory (see **Facilities and Resources**). Subjects will be directly observed for 3 hours after initial VCN dose and with phone follow-up calls 1-2 business days after starting the medication treatment period, and weekly thereafter. Follow-up phone calls will be completed within a two business day window before or after the target date. VCN plasma levels will be evaluated at end of both treatment periods on days 22 and 64 through a blood draw to monitor compliance. Blood samples will be stored at the University of Michigan Functional Neuroimaging, Cognitive & Mobility Laboratory until the study is finished. Data will be recorded on standard eCRFs and entered into the database for management and analysis by the **Biostatistics and Data Management Core.** Adverse events will be classified by organ system and assessed for causality. All potential possible adverse events will be discussed by the Executive Committee, and reported promptly to the IRB and NINDS.

Gait speed and postural control will be assessed at baseline, at the end of the first VCN/placebo administration period, at the end of the washout period, and at the end of the second VCN/placebo administration period. Gait and postural control will assessed by the **Clinical Resource Core (Core B)** using the Mobility Lab system that is already established (see Table 3; methodology for Mobility Lab will be as described in detail in Project II). MDS-UPDRS, Geriatric Depression Scale, Montreal Cognitive Assessment, WAIS Digit Span and Digit Symbol coding tests, and D-KEFS executive function/working memory tests will be administered as part of the evaluations. Subjects will be screened for suicidality with the C-SSRS before VCN treatment, weekly during phone follow-up, and at the end of treatment-washout periods.

[figure not shown]

Figure 5: Schematic Timeline for Experiment 3

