Analysis Method. For all aims, we will conduct exploratory analyses to examine the distributions of outcomes under each treatment, as well as individual and mean profiles over time. Graphical approaches such as boxplots and scatterplots with linear or non-linear (e.g., loess) methods will be used, allowing identification of outliers, linearity, and correlation of measurements within person and across time. If outcome data do not appear normally distributed, transformations will be employed. Because participants' outcomes will measured at more than one time point per person, our analyses will be based on linear mixed effects models (108-110). We expect no carryover since treatments will be spaced three weeks apart. Tests to compare treatments will be based on Wald and chi-squared tests based on maximum likelihood or restricted maximum likelihood methods. Alternative covariance structures (other than compound symmetry) will also be explored and model fit examined using the Akaike Information Criteria (AIC).

Potential Problems and Alternatives: All measures proposed for this experiment are well established in the University of Michigan Functional Neuroimaging, Cognitive and Mobility Laboratory and the **Clinical Resource Core**. The major foreseeable difficulties are subject recruitment and retention. We've had considerable success recruiting and retaining subjects in protocols involving up to 4 PET studies, serial evaluations, long-term follow-up (months to years), and subject clinical-psychometric-gait & balance evaluations as intensive as those proposed. We budget a 10% drop out rate in this study, which is typical of our experience in prior prospective studies and identical to the dropout rate in the recent AD study (89). A related concern would be unexpected difficulty with VCN tolerability, leading to excessive dropouts. The goal of the SA1 experiments is to find the lowest dose providing high  $\alpha 4\beta 2^*$  nAChR occupancy, which provides protection against this possibility. In the recent AD study, VCN was tolerated well at higher doses than we expect to employ. If tolerability is a problem, we would use a slower dose escalation regimen.

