4.1 General Study Design and Plan

This study is a single-center, randomized placebo-controlled double-blind crossover study of VCN in participants with PD to assess its effects on measures of gait, balance, and cognition. Participants were randomized 1:1 to one of two treatment sequences: placebo followed by VCN 0.5 mg b.i.d., or

VCN followed by placebo. Participants received an initial 0.25 mg dose or equivalent placebo following baseline evaluations and were monitored for 4 hours after initial study medication administration with total daily dose or equivalent placebo escalated over the next 2 days. Treatment periods were 3 weeks in duration and interrupted by a 3-week washout period. Participants underwent a standard evaluation at baseline, at the end of the first treatment period (week 3 [day 22]), at end of the washout period-beginning of the second treatment period (week 6 [day43]), and at the end of the second treatment period (week 9 [day 64]).

The schema below describes the main elements of the study design:

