4.3 Randomization and Blinding

Participants were randomized 1:1 to one of two treatment sequences: placebo followed by VCN 0.5 mg b.i.d., or VCN followed by placebo. A statistician prepared the randomization list using permuted blocks with random block sizes. The list with randomization number and treatment allocation was sent to the research pharmacy and a blinded list of randomization numbers was sent to the study coordinator. After patient consent was completed and eligibility confirmed, the coordinator assigned the next randomization number to the participant, and sent a prescription with participant ID and randomization number to the research pharmacist who dispensed the appropriate study medication. To mask drug, VCN pills or placebo were encapsulated in gelatin sheaths.

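### Counting all washout adverse events under the period-one treatment gives the first treatment a six-week window and the second three weeks; a split by on-treatment and washout time would be clearer

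*SAP*

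**What the plan says.** SAP section 4.1 sets out the design: "Treatment periods were 3 weeks in duration and interrupted by a 3-week washout period". Evaluations fall at baseline and on days 22, 43 and 64. SAP section 4.3 gives the allocation: "Participants were randomized 1:1 to one of two treatment sequences".

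On attribution, SAP section 9 says: "We will include adverse events that occurred in the washout period with the treatment given in period one". No time limit is attached. The treatment-emergent definition in SAP section 9.1 has a start (first treatment day) but no end. Safety data "will be summarized descriptively by treatment group for the Safety Population". The planned outputs in 9.1 are the number of AEs and the number and percentage of participants with at least one, by treatment. Related AEs and AEs causing discontinuation are summarised separately, and all treatment-emergent AEs are listed. No exposure-adjusted rate and no split between on-treatment and washout time is planned.

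Two protocol statements bear on how long VCN might act after the last dose. Under Specific Aim 1 (Procedures), which concerns the PET scans: "Five days is adequate to clear VCN". Under Specific Aim 2 (Procedures), the washout length rests partly on primate work with a related partial agonist, which found an effect of "ABT-089 on levodopa induced dyskinesias close to 2 weeks after dose cessation, well beyond the" half-life of that agent. The Analysis Method paragraph adds: "We expect no carryover since treatments will be spaced three weeks apart".

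**The concern.** If VCN is gone after five days, 16 of the 21 washout days in a VCN-first participant carry only background events, yet all of them enter the VCN column. The placebo column gains the same kind of time from placebo-first participants. Equal background added to both columns makes the two treatments look more alike in relative terms.

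This matters somewhat because the protocol says (Innovation) that VCN had not been tested in PD and (Specific Aim 1, Potential Problems) that tolerability may be an issue. Specific Aim 1 gives VCN to PD participants first but describes no placebo comparison, so the crossover supplies the project's placebo-controlled tolerability contrast. SAP section 2.2 places safety against placebo within the scope of the analyses.

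**Working it through.** **The plan's own figures.** With a half-life of about 24 hours, the fraction left after 5 days is 0.5^5 = 3.1%, so about 97% is cleared and the five-day statement reproduces. Day 22 to day 43 is 21 days, matching the stated washout.

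**Time credited to each treatment.** Take one participant per sequence, both completing. Each treatment is credited with 21 + 21 days where it comes first and 21 where it comes second: 63 days. Let W be the days after the last dose during which the VCN event rate persists. Credited VCN days at background rate are 21 − W:
- W = 5: 16 of 63 (25%)
- W = 14: 7 of 63 (11%)
- W = 21: 0 of 63

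**Rate ratio shown under the SAP rule.** Ratio = [RR × (42 + W) + (21 − W)] / 63. RR is an assumption, as is a constant background rate.
- RR 2.0, W = 5: (94 + 16)/63 = 1.75
- RR 2.0, W = 14: (112 + 7)/63 = 1.89
- RR 2.0, W = 21: 126/63 = 2.0
- RR 1.5, W = 5: (70.5 + 16)/63 = 1.37
- RR 3.0, W = 5: (141 + 16)/63 = 2.49

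**AE counts.** Take 33 participants (SAP section 5) and an assumed 10% background risk per three weeks, so the hazard per three weeks is −ln(0.9) = 0.1054. Use RR 2.0 and W = 5.
- SAP rule: placebo 33 × 0.1054 × 1.5 = 5.22; VCN 5.22 × 110/63 = 9.11; difference 3.89.
- On-treatment only: 6.95 v 3.48; difference 3.48.
- Washout only, by period-one treatment: VCN 16.5 × 0.1054 × 26/21 = 2.15; placebo 16.5 × 0.1054 = 1.74; difference 0.41.

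The parts sum to the whole (3.48 + 0.41 = 3.89). A window ending 5 days after the last dose also gives 3.89. The count difference is not diluted.

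**Participants with at least one AE.** Under a constant hazard, the risk is 1 − exp(−hazard × rate-weighted time), averaged over the two sequences. For 10% background, W = 5 and the SAP rule, VCN-first participants have 2 × 26 + 16 = 68 background-equivalent days, so 1 − exp(−0.1054 × 68/21) = 28.9%. VCN-second participants have 19.0%. The mean is 24.0%. Placebo is the mean of 19.0% and 10.0%, or 14.5%. Entries are VCN v placebo (difference in points from unrounded values; ratio), all at RR 2.0.

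| Background per 3 weeks | Effect lasts (W) | SAP rule | Window matched to W | On-treatment only |
|---|---|---|---|---|
| 10% | 5 days | 24.0 v 14.5 (9.5; 1.65) | 21.0 v 11.1 (9.9; 1.89) | 19.0 v 10.0 (9.0; 1.90) |
| 10% | 14 days | 25.5 v 14.5 (11.0; 1.76) | 24.3 v 13.1 (11.3; 1.86) | 19.0 v 10.0 (9.0; 1.90) |
| 30% | 5 days | 59.7 v 40.5 (19.2; 1.48) | 54.8 v 32.8 (22.0; 1.67) | 51.0 v 30.0 (21.0; 1.70) |
| 30% | 14 days | 62.0 v 40.5 (21.5; 1.53) | 60.3 v 37.4 (22.9; 1.61) | 51.0 v 30.0 (21.0; 1.70) |

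Ratios fall in every row. Against the matched window, the difference in percentages shrinks little at 10% background and more at 30%. Against on-treatment time alone, it shrinks only in the 30%, 5-day row.

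**The case against.** The best defence is that the rule is pre-stated and symmetric, and that it feeds a descriptive summary. The SAP plans no rate ratio, and one of its two main outputs, the number of AEs, keeps its treatment difference in full. Related AEs, discontinuations and individual listings are reported as well. All of this stands and limits the harm, although the related-AE summary depends on investigator judgement of causality.

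A reader might infer that anything after day five of washout is wrongly attributed to VCN. The documents do not support that. The five-day figure was written for clearance before a PET scan. The crossover washout has a separate rationale that allows for effects near two weeks, and being free of drug is not the same as being free of effect. If effects last 14 days, a 5-day cut-off gives a count difference of 3.89 in the example above, against 4.64 under the SAP rule, because real drug events leave the VCN column.

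A window running past the last dose in both periods would also need AE collection after day 64. The text available describes no later contact, though the schedule appendix is not included in it, so this cannot be settled here.

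**Conclusion.** The surviving point is modest. The SAP rule gives unequal AE windows, six weeks for the first treatment and three for the second, with no split or person-time to let a reader see the effect. Relative measures are pulled towards 1. Differences in participant percentages narrow mainly when background events are common, and differences in counts are preserved.

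A reader might go further and conclude that the rule biases the comparison in favour of VCN, or that a true excess will generally look smaller than it is. Neither follows: the allocation is 1:1, both columns gain the same extra time, and the count excess is unchanged.

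The 25% and 11% shares come from the documents' own durations and assume that everyone completes both periods. The ratios and percentages also rest on an assumed rate ratio, background risk and constant hazard, none of which the documents give. If VCN effects last the whole washout, the rate ratio is not diluted at all. This is an inexpensive improvement in reporting, not an error that threatens the trial's conclusions.

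**What to change.** In SAP section 9, add a table of AEs by treatment with two parts:
- **On-treatment:** first to last dose in each period, which gives VCN and placebo the same planned three-week window.
- **Washout:** by period-one treatment, with time since last dose shown, so that no single 5-day cut-off decides attribution.

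Give participants at risk or person-time for each column, which also deals with dropouts and shifted visit dates. Keep the present combined summary alongside, so every event stays reported.

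This should need only AE start dates and dosing dates. The cost is one extra table and fewer events per column, so each column will be less precise than the combined one.

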9.1 Adverse Events

Treatment-emergent adverse events are AEs that start on or after the first study day treatment is administered. The causal relationship of the AE to the study drug is determined by the site investigator as "not related" or "related". Adverse event severity grades are reported according to the Common Terminology Criteria for Adverse Events (CTCAE) Version 4.0. If the CTCAE does not have a grading for a particular adverse event, the severity of the event is reported by the investigator as mild, moderate, severe, or very severe. In the case of multiple occurrences of the same AE within the same subject, AEs will be summarized according to the maximum severity reported for each body system and overall.

Descriptive summary statistics for treatment-emergent AEs will be reported. The number of treatment-emergent AEs and the frequencies (number and percentage) of participants with one or more treatment-emergent AE will be summarized by treatment group, overall, by severity, and by body system. Coding of adverse events into body system was performed by the study chair for adverse events and by the medical monitors for serious adverse events. All treatment-emergent AEs related to study drug will be summarized, as will the frequencies of participants with one or more treatment-emergent AE related to study drug. Similarly, all treatment-emergent AEs causing study

discontinuation, and frequencies of participants experience these, will be summarized.

A subject listing of all treatment-emergent AEs and treatment-emergent AEs causing study discontinuation will be presented.

In accordance with clincaltrial.gov reporting requirements, the following table summarizing adverse events is required and will be provided:

• Other (Not Including Serious) Adverse Events: A table of anticipated and unanticipated events (not included in the serious adverse event table) that exceed 5% within either treatment group, grouped by organ system, with number and frequency of such events in each treatment group.

AEs that occurred after consent and before treatment will be listed.

The summary statistics will be produced in accordance with section 9.

